5.0 Study Procedures

An overview of the study procedures can be found in Appendix 3.

5.1 Pre-Treatment

The pre-treatment phase of this study consists of obtaining informed consent, an initial evaluation and enrollment process, as well as a screening for eligibility.

5.1.1 Screening and Informed Consent

The study will be described in detail to participants and their parents/legal guardians at an initial visit. If the participant and family agree to participate in the study, the applicable assent, consent and HIPAA documents will be signed (see Appendix 4). After informed consent has been obtained, a screening assessment will be performed. The screening assessment will include a medical history, physical examination and laboratory tests. The site psychologist will also administer the primary outcome measures (see section 5.1.4.1) and an abbreviated IQ measure which is estimated to take 50 minutes to complete. To be eligible to participate in the treatment phase, patients must have an impairment on at least one of the primary outcome measures of visual spatial learning or sustained attention (≥ 1 SD below the normative mean) and an IQ equal to or above 70. Unless the patient has undergone an IQ test within six months of screening, IQ will be assessed using the Wechsler Abbreviated Scale of Intelligence (WASI; Wechsler, 1999). If the participant has recently completed an IQ test (within six months of screening), then this score will be used for the purposes of screening. Examples of acceptable IQ tests include (but are not limited to) the WASI, the Wechsler Intelligence Scale for Children 4th Edition (WISC-IV), and the Stanford-Binet Intelligence Scales 5th Edition (SB-V).

If the child fails to satisfy the screening criteria, parents will be verbally informed of the reason why the child did not meet the criteria. If the reason for exclusion was a Full-Scale IQ less than 70, parents will be verbally informed of the range of the child's IQ score and that it may indicate the presence of an intellectual disability. Parents will be advised that only a brief assessment of IQ was conducted and that the child's performance may vary due to motivation, attention and fatigue. It will be recommended to parents that their child undergo a full IQ assessment to obtain further information about their child's intellectual functioning. Upon request, results of the IQ test will be provided to parents in a written report.

5.1.2 History and Physical Examination

A complete medical history and physical examination (including neurological examination) will be performed initially to confirm each participant's NF1 diagnosis and to document any complications that they might have from the disease. Height, weight, head circumference, blood pressure, and pulse will be recorded. Patients will also be given a list of medications to avoid while on this study. To be eligible participants must have not taken any stimulant medications for at least 30 days or more and agree to remain off stimulant medication for the duration of the study.

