Given that general intellectual functioning is not the key explanation for the pattern of observed academic failure, it is likely that these specific neurocognitive deficits contribute to or are responsible for the characteristic profile of children with NF1. As such, these NF1 associated deficits may negatively impact on daily living skills, academic performance, employment opportunities and quality of life (Graf, Landolt, Mori & Boltshauser, 2006; Page, Page, Ecosse, Korf, Leplege et al., 2006). Despite the significant negative impact of this disorder on cognitive and behavioral functioning, only one study has reported on treatment outcomes (Mautner et al., 2002). The results of this study demonstrated that stimulant medication was effective in treating the behavioral symptoms of ADHD in children with NF1. To date, no studies have examined the

effects of interventions on the cognitive functioning of children with NF1. Clearly, there is a need to investigate interventions that can improve cognitive impairments associated with NF1.

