4.2 Inclusion Criteria

- Males or females aged between 8 years to less than 16 years at time of screening who meet NIH diagnostic criteria for NF1 (Appendix 1);
- Participants must have a full-scale IQ of 70 or above. In cases where there is a statistically significant difference between verbal IQ and performance IQ (.05 level as determined by Table B3 in the WASI manual), participants will be eligible if at least one of these quotients is 70 or above;
- Participants must have a cognitive impairment defined as having a score of at least one standard deviation or more below the population mean on one or more of the primary objective outcome measures (i.e., impaired on a measure of visual spatial learning and/or sustained attention);
- Participants must be medically stable;
- Participants who are on a stable dose of methylphenidate and/or dextroamphetamines for at least one month prior to screening and who will remain on the same dose for the duration of the study (see Section 4.3 for exclusion criteria regarding other psychotropic medication, i.e. medication capable of affecting the mind, emotions or behavior)
- Hepatic function: Participants must have adequate liver function defined as at least 3 of the 4 liver function tests to be $< 2 \times$ upper limit of normal for age according to institution standards (AST, ALT, Direct bilirubin, Indirect bilirubin [computed from total bilirubin and direct bilirubin]) and no tests should be $>5 \times$ upper limit of normal for age;
- Renal function: Participants must have adequate renal function defined as serum creatinine $\leq 1.5 \times$ upper limits of normal for age, and BUN $\leq 1.5 \times$ upper limits of normal for age or a creatinine clearance of greater than 70 ml/m/1.73m²;
- Hematologic function: Participants must have an absolute neutrophil count of $> 1,000$, a hemoglobin ≥ 10 gms/dl, and a platelet count $> 100,000$ on study entry;
- Participants must sign all required documents, including informed assent and HIPAA documents;
- Female participants of childbearing age should not be pregnant, must have a negative pregnancy test before initiation of treatment, and take appropriate birth control precautions to participate in this study.

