4.3 Exclusion Criteria

- Full-scale IQ less than 70. In cases where there is a statistically significant difference between performance IQ and verbal IQ (.05 level), patients will be excluded if both quotients fall below 70;
- Individuals that are not cognitively impaired on at least one of the primary objective outcome measures;
- Individuals with insufficient English to complete the assessments;
- Participants taking psychotropic medication other than methylphenidate and/or dextroamphetamines (see Section 4.2). Appendix 2 contains a list of common psychotropic medications. These patients are eligible if, as clinically indicated, they cease medication for at least 30 days prior to screening and remain off these medications for the duration of the study;
- Participants with intracranial pathology such as epilepsy, diagnosed head injury, hydrocephalus or progressive intracranial tumors (children with asymptomatic or static lesions will be eligible);
- Participants who are pregnant or breastfeeding;
- Participants who have received any investigational drug (other than sirolimus) within 30 days of screening;
- Participants who have recently taken sirolimus. These participants will be eligible after a washout period of at least three months;
- Participants who have recently taken Lovastatin. These participants will be eligible after a washout period of at least three months;
- Participants with significant hepatic, renal or hematologic function as previously defined;
- Participants with a history of neuromuscular disease, excluding hypotonias thought to be associated with NF1;
- Participants with a clinically significant unrelated illness, which in the judgment of the principal or associate investigator, would compromise the participant's ability to tolerate the medication or potentially interfere with the participant's ability to participate in the required testing;
- Low cholesterol (lower limit of a total cholesterol of 90mg/dl).

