5.2.3 Off-Study Criteria (Note: See Section 6.6 for modifications for toxicity information)

A participant will be taken off the study for the following reasons:

- The participant refuses further treatments and/or wishes to withdraw from the study;
- For participants concurrently taking stimulant medications (methylphenidate and/or dextroamphetamines), they will be withdrawn from the study if they stop or change the dose or type of stimulant medication before their final study visit;
- It is deemed in the best interest of the participant to stop the study by the research team;
- Serious protocol violation or non-compliance as determined by the principal investigator or research team;
- The development of significant drug toxicity, such as recurrent grade 3 or 4 toxicity after dose reduction; and/or persistent grade ≥ 2 toxicity for >10 days without administration of the drug;
- The development of a concurrent serious medical condition that might preclude or contraindicate the administration of Lovastatin;
- Death.

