6.4 Drug Dosage and Possible Interactions

The selection of the maximum dose of Lovastatin to be used in this study, 40 mg/day, is based on the tolerability of the drug when used for heFH and the results of the Phase I study examining safety and tolerability of Lovastatin in children with NF1 (Acosta et al., submitted). Participants will commence at 20 mg/day for two weeks and escalate to the 40 mg/day dose in week 3.

Approximately 40% of children with NF1 are diagnosed with comorbid ADHD, many of whom are treated with psychostimulant medication such as methylphenidate and/or dextroamphetamines. In order to minimize recruitment bias and ensure recruitment targets are met, patients taking methylphenidate and/or dextroamphetamines will be eligible for this study.

The predominant metabolic pathway of methylphenidate is de-esterification to form pharmacologically inactive d- or l-ritalinic acid (Patrick et al 1987). Metabolism of methylphenidate when used by oral administration undergoes a stereoselective clearance to ritalinic acid (CES1A1 is the major enzyme responsible) before entering systemic circulation (Sun et al, 2004). Methylphenidate does not use the microsomal cythochrome P450 in the liver for its metabolism (Sun et al 2004; Patrick et al 1987). Dextroamphetamines are metabolized by the cythochrome P450 in liver. However the isoenzyme responsible for its metabolism is the CYP2D6 (Adderall Medication Guide, Shire, Nov. 2010). Instead, lovastatin is metabolized by the CYP3A4 (Ritalin® Medication Guide, Novartis, 2010). There are not described interactions or competitive mechanism between dextroamphetamines and lovastatin.

Although limited by a small sample size, results of the Phase I study provide some evidence for the inclusion of patients on stimulant medication (Acosta et al., submitted). A total of 23 patients with NF1 (10-17 years of age) completed 12 weeks of treatment with Lovastatin. Nine patients had a diagnosis of ADHD and five of these patients were taking a stable dose of stimulant medication during the course of the study. Calculation of Reliable Change Index for individuals indicated significant improvements on both verbal and nonverbal memory measures in approximately 40% of participants regardless of whether they were off or on methylphenidate.

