The list of psychotropic medications is quite extensive. As many psychotropic medications may interact with the metabolism of Lovastatin, e.g. Fluoxetine, patients taking psychotropic medications other than stimulant medications will be excluded from the study. Also, participants on other medications to control behavior (including Straterra) and anticonvulsants will not be eligible to participate in the study as these medications are known to affect cognition and learning and, thus, confound the results of the study. However, these participants may be eligible if they cease medication for at least 30 days prior to screening and remain off these medications for the duration of the study. Importantly, all participants must still demonstrate impairment on either of the primary outcome measures at the screening assessment and satisfy all other inclusion criteria to be enrolled in the study.

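### Section 5.1.2 bars children on stimulants, while sections 4.2, 4.3, 5.2.3 and 6.4 admit those on a stable dose of methylphenidate or dextroamphetamine

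*Protocol*

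**What the plan says.** Section 5.1.2 of the protocol, on the history and physical examination, contains an eligibility rule: "To be eligible participants must have not taken any stimulant medications for at least 30 days or more". The sentence goes on to require that the child stay off stimulants throughout the study.

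Four other sections say something different:

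- Section 4.2 lists as eligible: "Participants who are on a stable dose of methylphenidate and/or dextroamphetamines for at least one month prior to screening", if the same dose is kept for the whole study.
- Section 4.3 excludes children on psychotropic drugs, but exempts methylphenidate and dextroamphetamine by name. Its rule of 30 days off before screening, and off thereafter, is for the other psychotropics.
- Section 5.2.3 says of children on these stimulants that "they will be withdrawn from the study if they stop or change the dose or type of stimulant medication before their final study visit".
- Section 6.4 gives the reason for admitting them: "In order to minimize recruitment bias and ensure recruitment targets are met, patients taking methylphenidate and/or dextroamphetamines will be eligible for this study". It supports this with metabolic arguments and Phase I experience, and then adds that "patients taking psychotropic medications other than stimulant medications will be excluded from the study".

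Section 7.0, identical in the protocol and the SAP, also names ADHD with or without stimulant treatment as a possible exploratory subgroup. No text ranks these sections or reconciles them.

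**The concern.** A child on a steady dose of methylphenidate is eligible under 4.2, 4.3 and 6.4 and ineligible under 5.1.2. The 5.1.2 sentence covers any stimulant, so it cannot be read as applying only to drugs outside the permitted pair. It is worded as a condition of eligibility and sits in the section that staff use at the first examination, so a site could reasonably apply it.

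Such a site has two ways to comply. It can screen these children out, which works against the purpose given in 6.4. Or it can have them come off the drug to qualify, although section 1.1 reports that "stimulant medication was effective in treating the behavioral symptoms of ADHD in children with NF1". The protocol offers no rationale for doing that to children.

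Sites reading different sections would enrol different populations and could screen similar children in different medication states. That matters because entry depends on scoring at least one SD below the norm on a cognitive test, and section 1.9 describes such tests as sensitive to drug-induced improvement. A site following 5.1.2 would also contribute no on-stimulant children to the exploratory ADHD subgroup.

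**Working it through.** **1. The rules side by side**

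| Section | Child on a stable permitted stimulant at screening | Same child stops the drug after entry |
|---|---|---|
| 5.1.2 | Not eligible | Abstinence is required |
| 4.2 | Eligible | Breaks the constant-dose condition |
| 4.3 | Not excluded | Not addressed |
| 5.2.3 | Presupposes such children are enrolled | Withdrawn |
| 6.4 | Eligible | Not addressed |

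Under 5.1.2 the stimulant rule in 5.2.3 would have nobody to apply to. A child enrolled under 4.2 and then taken off the drug to satisfy 5.1.2 would have to be withdrawn under 5.2.3. The two rules cannot both operate.

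**2. Which text is wrong.** Sections 4.2, 4.3, 5.2.3 and 6.4 agree, and 6.4 argues the case. The 5.1.2 pattern (30 days off, then remain off) is the one that 4.3 and 6.4 apply to other psychotropics. The intent is therefore clear, and 5.1.2 is the outlier.

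**3. The plan's own sample size, for context.** Inputs from section 7.0: difference 0.5 SD, two-sided alpha 0.05, power 0.80, dropout 10%. The normal approximation gives 63 per arm. The t-test solution is 63.8, so 64 per arm, with power 0.801. For dropout, 128 / 0.90 = 142.2, against 142 stated. The plan's figures reproduce, and none of them depends on the stimulant rule.

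**4. How many children are affected.** The documents give no stimulant share for the target population. The nearest figure is Phase I in section 6.4: of 23 patients, nine had ADHD and "five of these patients were taking a stable dose of stimulant medication during the course of the study". The assumption is that this share carries over.

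- Share: 5 / 23 = 0.217; Clopper-Pearson 95% CI 0.0746 to 0.4370.
- Of 142: 142 × 0.217 = 30.9, with limits 142 × 0.0746 = 10.6 and 142 × 0.4370 = 62.1. That is about 31 children (11 to 62).
- By another route, the 40% ADHD figure in 6.4 times the Phase I 5 of 9: 0.40 × 5/9 = 0.222, and 142 × 0.222 = 31.6.
- Sensitivity: with 40% ADHD and an assumed 25% to 75% of those treated, the share is 10% to 30%, or 14 to 43 of 142.

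**5. Upper case for recruitment.** Suppose every site followed 5.1.2 by screening these children out. Otherwise-eligible candidates needed to enrol 142 = 142 / (1 − share):

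- 142 / (1 − 0.217) = 181.4, about 39 more than 142
- 142 / (1 − 0.0746) = 153.4, about 11 more
- 142 / (1 − 0.4370) = 252.2, about 110 more

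**The case against.** The contradiction itself is not in dispute. The case against giving it weight is as follows.

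*Sites will probably not be misled.* The sections headed inclusion and exclusion criteria agree, 5.2.3 gives a working rule for stimulant users, and 6.4 explains the intent. This is fair. The documents show that sites could diverge, not that they will. The case in which every site follows 5.1.2 is a bound, not a forecast.

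*The harm is overstated.* A child who stops the drug for 30 days and then enrols still counts toward 142, so only outright exclusion costs recruitment. This stands. Section 5.1.2 also sets a condition and does not instruct anyone to withdraw treatment, so the participant-protection concern is an inference. It is a reasonable one, because stopping is the only way a treated child can satisfy the sentence.

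*The size rests on thin data.* This stands. It comes from five children aged 10 to 17, whereas this trial takes ages 8 to under 16 and selects for cognitive impairment. The confidence interval does not cover that difference. The 22% check is not independent either: it reuses the same five children, and the Phase I ADHD share of 9/23 = 39% nearly equals the 40% figure.

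*Other stimulant wording is loose.* Section 6.4 exempts stimulants in general where 4.3 names two, and Appendix 2 lists stimulants without marking which are allowed. The 6.4 wording reads naturally as shorthand for the two drugs it has just discussed, and 4.3 controls how the appendix is used. This does not excuse 5.1.2.

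*Inference is untouched.* Correct. Section 5.1.5 stratifies randomization by site, so a site-level difference in eligibility does not by itself bias the treatment comparison. The subgroup at stake is exploratory and conditional on sufficient cases.

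**Conclusion.** The concern holds. Section 5.1.2 is wrong as written: it reverses the eligibility of children whom 4.2, 4.3, 5.2.3 and 6.4 admit, and nothing in the protocol resolves the conflict.

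If the Phase I share carries over, about 31 of 142 children (11 to 62) have an eligibility status that depends on which section is followed. The range is wide, and the age and selection differences add uncertainty it does not show. The recruitment figures are an upper case that assumes every site obeys the wrong sentence.

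The consequence is for who is enrolled, consistency between sites, generalizability and participant protection. The planned sample size, the power and the validity of the randomized comparison are not affected. It should be fixed because the error is plain and the remedy is small.

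**What to change.** Delete the stimulant sentence in 5.1.2 and replace it with a cross-reference to 4.2 and 4.3 that restates the rule:

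- A child whose methylphenidate and/or dextroamphetamine dose has been stable for at least one month before screening is eligible, provided it stays the same for the study.
- Any other psychotropic must have been stopped, where clinically indicated, at least 30 days before screening and not be restarted during the study.

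Send every site a memo stating this rule.

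The cost is one amended sentence and one memo. No patients, visits or analyses are added.

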5.1.3 Laboratory Studies

A pre-treatment enrollment laboratory test will be performed at least two weeks prior to commencing the study medication. The following studies will be performed:

- Hematology: Complete blood count (CBC);
- Chemistries: Blood urea nitrogen (BUN), creatinine, alanine aminotransferase (ALT), aspartate aminotransferase (AST), CPK and, Lipid profile (HDL, Cholesterol, LDL, Triglycerides), total bilirubin and direct bilirubin (indirect bilirubin will be computed from total and direct bilirubin serum measurements);

- Urine Pregnancy Test: A urine pregnancy test will be performed on all females of childbearing age before commencing study medication and at weeks 8 and 16.

In order to ascertain an accurate lipid profile, participants will fast overnight before their laboratory tests are performed. This will apply to all lipid assessments conducted during the study period.

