5.1.5 Randomization

Following a successful screening period, the participant will be randomized to one of the two treatment groups: Lovastatin or placebo. Randomization will be implemented by the Data Coordinating Center for this trial utilizing a permuted blocks approach.

Randomization will be stratified by clinical site, to ensure adequate balance between the treatment groups, overall and at each site. Password protection will be implemented to ensure that only certified clinical center personnel are allowed to randomize patients and access the database. At the time of randomization, each participant will be assigned a unique medication kit identification number that will be used throughout the duration of the study.

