5.2 Treatment Visits

5.2.1 Dose Schedule and Prescription

Eligible participants will be dispensed 20mg of Lovastatin or the placebo at the initiation of treatment. Participants will be given directions to take the medication once daily after dinner time. Given that Lovastatin has a strong odor; participants will be required to swallow the capsule whole without breaking the seal. Participants will take one tablet (20mg Lovastatin) per dose for two weeks; and increase to two tablets per dose during the following weeks (40 mg Lovastatin). Participants will continue on the same dosage for a total of 14 weeks. In order to assess medication compliance, participants will be required to complete pill diary forms. All participants will be provided with a complete list of medications and products that have detrimental interactions with Lovastatin that must be completely avoided while being treated with Lovastatin (see Appendix 6).

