5.2.2 Clinical Evaluation

Throughout the treatment phase of the study, participants will be clinically evaluated every 4 weeks (\pm 4 days) by a neurologist or a qualified physician at each site. At each visit, an interim medical history and physical examination (including a neurological examination) will be performed. Height, weight and body surface area will be obtained. Participants will be assessed for toxicity/side effects and safety labs will be performed as specified in section 5.1.3 every 4 weeks (\pm 4 days). Medication compliance will also be assessed at these visits. Pill diaries will be

reviewed and a pill count will be performed and recorded. At the end of the study or the treatment period, all unused medication will be collected and disposed of properly on a per site basis according to clinical procedures and guidelines.

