6.6 Modifications for Toxicity

Participants who experience grade 2 toxicity related to Lovastatin will have Lovastatin withheld until the toxicity resolves (grade ≤ 1) and then restarted at the same dose level. If the grade 2 toxicity recurs, the dose will be withheld again until the toxicity resolves (grade ≤ 1) and then reduced to 50% of the dose. If the grade 2 toxicity recurs, the participant will be taken off the protocol. The participant will be evaluated by the principal investigator.

Participants who experience grade 3 or 4 toxicity related to Lovastatin will have their dose withheld. If the toxicity returns to grade ≤ 1 within 10 days, the participant may resume Lovastatin at a dose reduced by 50%. If the toxicity persists at grade ≥ 2 for >10 days without administration of Lovastatin or the grade 3 or 4 toxicity recurs at the lower dose, the participant will be removed from the study.

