6.11 Risks and Protection from Risks

Individual risks in this study are associated with the use of Lovastatin, laboratory tests (blood drawn) and with neuropsychological testing.

Lovastatin has been shown to be safe and effective in a pediatric population for treatment of familial HeFH. The FDA has approved Lovastatin (40mg/day) for treatment of HeFH in children and it is believed to be safe to extend to other potential uses. The most frequent side effects of Lovastatin are muscular pains, weakness and tenderness, and gastrointestinal conditions such as

abdominal pain, flatulence, diarrhea and constipation, and are reversible once the medication has been discontinued. Participants will be provided with a list of drug and food items that they should avoid while on study medication. All participants will be monitored for adverse events as described in Section 6.7. Participants who experience adverse events related to the study medication will have study medication withheld and/or modified as outlined in Section 6.6. Additionally, there will be regular monitoring and clinical evaluation.

In the 24 patients that were evaluated for the Phase 1 Lovastatin study, few patients' total cholesterol dropped below 100, and in all cases, the HDL:LDL ratio was within normal limits. In all cases total cholesterol returned to baseline after the treatment. From a clinical perspective, decreased LDL is one of the desirable outcomes of using Lovastatin. There is no evidence of increase risk or harmful consequences for a temporal decrease of LDL levels. Since this is a 16 week study (plus follow-up), transient decrease in lipid profile levels will not change the risk for this patient population.

Since the long-term effects of lowering lipid levels in the children on Lovastatin are unknown at this time, having normal range cholesterol (cholesterol \geq 90 mg/dL) is a criteria for enrollment. In addition, a lipid profile is checked at baseline and at weeks 4, 8, 12, 16 and 24. If levels drop below 80 mg/dL, the site should notify the protocol team for guidance. If other lipid profile levels drop below normal values, the site should also notify the protocol team for guidance.

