APPENDIX 3: Study Evaluation Before, During, Post Treatment and Follow-Up

Observation	Pre-treatment	2 weeks*	4 weeks (2 titrated & 2 weeks full dose)	8 weeks	12 weeks	Post-treatment 16 weeks	Follow-up (8 weeks off medication)
Phone Calls		X					
Hx and Physical	X		X	X	X	X	X
CBC	X		X	X	X	X	X
Chemistries	X		X	X	X	X	X
Neuropsychological measures	X					X	X
Pregnancy testing	X			X		X	
Side-Effects/Toxicity (Check List)		X	X	X	X	X	X
Drug compliance		X	X	X	X	X	

NB. Chemistries: Blood urea nitrogen (BUN), creatinine, glucose, alanine amino transferase (ALT), aspartate amino transferase (AST), total and direct bilirubin, CPK, Lipid profile (HDL, Cholesterol, LDL, Triglycerides). Indirect bilirubin will be computed from total and direct bilirubin serum measurements.

*Use CRFs as a guide with questions for phone follow-up

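### Section 5.1.3 sets a minimum age but no maximum for the pre-treatment blood count and chemistry labs, so a first dose can rest on out-of-date results

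*Protocol*

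**What the plan says.** - **Timing of the labs.** Protocol 5.1.3: "A pre-treatment enrollment laboratory test will be performed at least two weeks prior to commencing the study medication". The panel is a complete blood count, BUN, creatinine, ALT, AST, CPK, bilirubin and a lipid profile. A urine pregnancy test must precede study medication, also with no stated maximum age.
- **Where they are drawn.** Protocol 5.1.1 puts them at screening: "The screening assessment will include a medical history, physical examination and laboratory tests".
- **What follows.** Protocol 5.1.5: "Following a successful screening period, the participant will be randomized to one of the two treatment groups". No length is given for that period, nor for the time from randomization to first dose.
- **What they decide.** Section 4.2 sets hepatic, renal and hematologic limits, and section 4.3 excludes low cholesterol. The hematologic limit applies on study entry. The others carry no date.
- **Next scheduled labs.** Protocol 5.2.2: "safety labs will be performed as specified in section 5.1.3 every 4 weeks", with a window of 4 days either side. Appendix 3 has one pre-treatment column, a phone contact at week 2 and labs at week 4.
- **Possible lipid recheck.** Protocol 6.11: "a lipid profile is checked at baseline and at weeks 4, 8, 12, 16 and 24".
- **Use of the results on treatment.** Protocol 6.6: "Participants who experience grade 2 toxicity related to Lovastatin will have Lovastatin withheld until the toxicity resolves".

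The SAP repeats protocol text from the end of section 6.11 to section 9.1 and adds nothing on lab timing.

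**The concern.** A timing rule for eligibility labs should keep the results close to first dose. This one keeps them away from it: a single draw 10 days before treatment breaks the rule, while a single draw four months before satisfies it.

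Two things are at stake, both at the level of the individual child.

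1. **Clearance to start.** The limits in section 4.2 protect the child only if they hold when drug is first taken. An old result shows that they held once.
2. **Attribution on treatment.** Section 6.6 turns on whether a toxicity is related to Lovastatin. Section 4.2 allows one of the four liver tests to lie between 2 and 5 times the upper limit of normal, and Appendix 7 grades ALT or AST above 2.5 and up to 5 times that limit as grade 2. Neither 4.2 nor 4.3 sets a CPK limit. A child may therefore enter with a value already in the grade 2 range. A recent pre-dose value is then the main laboratory evidence on whether a week-4 elevation is new, and the older it is, the less it says.

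**Working it through.** The plan states no figure to reproduce. The check has two parts: a search for a limit elsewhere, then day arithmetic.

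**1. Does any other section supply a maximum or a repeat?**

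| Section | What it offers | Does it cap lab age at first dose? |
|---|---|---|
| 4.2 | Hematology limits on study entry | No: hematology only, not tied to first dose |
| 5.1.1 | Labs are part of screening | No: no time limit to first dose |
| 5.1.4 | Neuropsychological measures within one month of enrollment and before treatment | No: does not cover labs and runs from enrollment |
| 5.1.5 | Randomization after screening | No: no length stated |
| 5.2.2 | Labs every 4 weeks on treatment | No: starts after first dose |
| 6.11 | Lipid profile at baseline | No: lipids only, undated, perhaps a separate check |
| Appendix 3 | One pre-treatment column | No: no window shown |

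The protocol does set time limits elsewhere: six months for a prior IQ test (5.1.1), one month for the neuropsychological battery (5.1.4) and 4 days either side for treatment visits (5.2.2). The safety labs before first dose have none.

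**2. How old can the results be?**

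Inputs: L is the age of the labs in days at first dose. Section 5.1.3 gives L of at least 14. The week-4 draw falls on day 28, with a window of day 24 to day 32 (5.2.2).

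Formula: gap from the pre-treatment labs to the week-4 draw = L + day of that draw.

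- As written, nominal visit: 14 + 28 = 42 days or more. Early edge: 14 + 24 = 38 days or more. No upper limit.
- With a 28-day maximum: at most 28 + 28 = 56 days. Late edge: 28 + 32 = 60 days.
- With a 14-day maximum: at most 14 + 28 = 42 days. Late edge: 14 + 32 = 46 days.

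The 28 days on treatment are fixed by the visit schedule. Only L changes.

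**3. What would a cap change in practice?**

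This depends on how long starts are delayed, which the documents do not give. The values of L below are assumptions.

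| Assumed L (days) | Gap to week 4 as written | Gap with a 28-day maximum |
|---|---|---|
| 30 | 30 + 28 = 58 | at most 56 |
| 60 | 60 + 28 = 88 | at most 56 |
| 90 | 90 + 28 = 118 | at most 56 |
| 120 | 120 + 28 = 148 | at most 56 |

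At a 30-day delay the cap gains 2 days. The gain is material only if starts slip well past a month.

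**The case against.** The strongest reply is that the open-ended wait is only a literal possibility. Section 5.1.3 calls this an enrollment test, section 4.2 ties hematology to study entry, and section 5.1.4 places the baseline assessment within a month of enrollment, with a fresh review of the child's history. Together these suggest a short sequence. The two weeks may be lead time for results, or a slip for a two-week maximum. This bears on how often the problem would arise. It does not supply a ceiling: lead time explains the floor only, and if the sentence is a slip it says the opposite of what was meant.

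Two textual objections stand in part. The 6.11 sentence on lipids opens as an addition to the enrollment criterion, so it may mean a separate lipid check. Lipids are therefore the weakest part of the point. The single pre-treatment column in Appendix 3 does not prove a single draw, because it also covers neuropsychological testing that is split between screening and baseline. It leaves a repeat possible without requiring one.

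On harm, Appendix 7 grades liver tests and CPK as multiples of the upper limit of normal, so an old baseline does not change a grade. It affects only the judgment of relatedness, and withholding and restarting drug under 6.6 also informs that judgment. Entrants must be medically stable, significant unrelated illness is excluded, dosing starts at 20 mg, a side-effects checklist is done at week 2, and the placebo arm protects group comparisons. All of this stands and keeps the point modest.

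A reader might infer two stronger points that the documents do not support:

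- **That the dose step is the problem.** Section 5.2.1 says: "Participants will take one tablet (20mg Lovastatin) per dose for two weeks; and increase to two tablets per dose during the following weeks". This happens without labs, but that is a separate design choice, and a cap on pre-treatment lab age adds no week-2 labs.
- **That the transient AST elevations in section 1.5 show the danger.** They occurred on drug, so they say nothing about drift before the first dose. The same section reports no significant CPK or AST difference from placebo in a 48-week trial in boys.

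**Conclusion.** The point holds for the blood count and the liver, renal and CPK labs. Section 5.1.3 sets a floor of 14 days where a ceiling is needed, and nothing else in the protocol or SAP caps the age of these results or clearly requires a repeat. For lipids the position is less certain because of section 6.11.

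As written, the labs are at least 14 days old at first dose and at least 42 days before the nominal week-4 draw (38 at the early edge of the visit window), with no maximum. A 28-day limit would hold these to 28 and 56 days (60 at the late edge). The 28-day figure is a proposed choice, and the 60- to 120-day delays are assumptions for illustration.

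A reader might infer that children will in fact start on labs that are months old, or that the trial's conclusions are at risk. The documents support neither. They do not say how often starts are delayed or that organ function drifts in medically stable children, and power and the primary analysis are unaffected. What remains is a wrongly directed safety rule that weakens clearance and attribution for the individual child and is worth correcting because the correction is cheap.

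**What to change.** Reword section 5.1.3 so that the blood count and chemistry labs are drawn no more than 28 days before first dose, early enough for results to be reviewed before randomization and dispensing, and repeated if the start slips past that window. If the two weeks were meant as lead time, they can stay: a draw 14 to 28 days before first dose meets both limits. Add the window to the pre-treatment column of Appendix 3.

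As a minor refinement, time the already planned urine pregnancy test to the visit just before dispensing, and proceed only on a negative result. Sections 4.2 and 5.1.3 already require a test before treatment, section 4.2 requires birth control, and the test is repeated at weeks 8 and 16. This sets the timing of an existing test and adds no routine one.

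Cost: one sentence, one note in the schedule, and an occasional repeat draw or urine test when a start is delayed. Sample size, randomization and analysis do not change.
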